6.2 Secondary endpoints

The analysis for continuous secondary outcomes follows the analysis specifications of the primary outcome (see above), except when distributional assumptions are not met. In this case, a log-transformation will first be used and subsequently assessed with residual analyses. When log-transformations still show deviations from distributional assumptions, alternative distributions or non-parametric analysis will be considered. As for the analysis of the primary outcome, all regression analyses will be performed by adjusting for the same a priori defined prognostic factors and repeated measurements.

Binary secondary outcomes will be analyzed with mixed logistic regression analysis. Secondary count outcomes (e.g. the number of hypoglycemic events) will be analyzed with a generalized linear mixed model: the distributions utilized will depend on the observed distribution. Initial analysis will be performed with a negative binomial distribution. The distribution may show a high number of patients with zero events. If so, the distribution will be adjusted to either a zero-inflated Poisson distribution or a zero-inflated negative binomial distribution.²⁰ For binary and count outcomes, analyses with a random intercept will initially be performed, as these analyses may be performed under maximum likelihood estimation. Assumption for linearity will be assessed and adjustments will be made when necessary.

Secondary outcomes measured only once during follow-up (i.e. at 12 months) will be analyzed with linear, logistic and negative binomial regression models (as applicable) without adjustment for repeated measurements (i.e. regular linear and logistic regression). Results from linear models will be reported as a difference in means (with 95% Cls). For binary outcomes, results will be reported as odds ratios with 95% Cls. For negative binomial models for count outcomes, results will be reported as rate ratios with 95% Cls.

Secondary endpoints will be considered supportive and are not included in the formal testing strategy. P-values will therefore not be provided.

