3.1 Study arm 1: HCL as control treatment and DHFCL as index treatment

A recent cross over study of the index intervention treatment (DHFCL) showed a median mean TIR of 86% (SD 4%).¹ Previous studies show a mean TIR under HCL treatment of 70 to 78% (SD 16% to 17%). ²⁻⁴ To be conservative, we assume a 7% increase in mean TIR from 78% under the HCL control treatment (SD 17%) to 85% under the index intervention treatment (SD 4%), using the two sample t-test with unequal variances, two-sided significance level of 0.05 and a power of 90%. Accordingly, the required sample size for this arm is 68 per group. To allow for potential loss to follow-up and to address the main secondary endpoints, we include a sample size of 85 per group in this arm of the trial: 85 in the HCL control treatment group and 85 in the DHFCL index treatment group.

3.2 Study arm 2: MDI+FGM/CGM as control treatment and DHFCL as index treatment.

Previous studies showed a mean TIR under MDI+FGM/CGM treatment of 50-59% (SD of 12 to 20%).⁵ To be conservative again, we assume a mean TIR in the MDI+FGM/CGM control group of 70% (SD 20%) and for the DHFCL index intervention of 85% (SD 4%) (similarly as above), thus assuming a 15% increase in mean TIR due to the index intervention. Using the two sample t-test with unequal variances, two-sided significance level of 0.05 and a power of 90%, the required sample size for this arm is 22 per group. To allow for potential loss to follow-up and to address the main secondary endpoints we include a sample size of 35 per group in this arm of the trial: 35 in the MDI+FGM/CGM control treatment group and 35 in the DHFCL index treatment group.

4. Outcome measures

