6.1 Primary endpoint

The primary endpoint (mean TIR at 12 months) will be compared between the DHFCL treatment and the two control treatments. The analysis will be performed for each of the study arms (see above) separately. To obtain this comparison, a mixed model analysis for continuous outcomes will be performed with TIR at 3, 6, 9 and 12 months (hence forward referred to as time) as dependent variable. This is a linear regression model that includes a random intercept for center of inclusion and a residual covariance matrix to correct for multiple measurements per patient. The initial analysis will be performed with a heterogeneous autoregressive matrix that assumes different variances for each measurement, a constant correlation between adjacent measurements and consistently lowering correlation when time between measurements is longer. The first analysis will include time, treatment and an interaction between time and treatment as fixed effects. In the second analysis, correction for the predefined prognostic factors, i.e. TIR at baseline, patients age and sex, will be included in the analysis as fixed effects. As the primary endpoint comparison is defined at 12 months, a specific contrast will be included in the analysis to compare mean TIR at 12 months between DHFCL control treatments. Results will be reported as difference in mean TIR with 95% confidence intervals (CIs). P-values will only be reported for the primary analysis in the ITT population. Study arm 1 and 2 will be considered two separate trials in different populations and as such no multiplicity correction is planned for performing these two primary comparisons under a single study protocol. The p-value for study arm 1 and study arm 2 will each be separately compared to the threshold 0.05 to declare significance.

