The primary analysis may result in convergence problems when the residual covariance matrix is not correctly specified, given the data. In this case, the residual covariance matrix may be adjusted. Convergence problems may also arise for the estimation of the random intercept for center of inclusion when one or more centers include a low number of patients or when included patients from different centers show very similar outcome measurements. In this case, the random intercept may be excluded from the analysis and the addition of a variable representing academic centers versus peripheral centers may be added to the analyses models as a fixed effect. The regression model with residual covariance matrix is specifically chosen as the primary analysis, as it allows to incorporate all non-missing measurements of patients over time. Further details on missing outcomes are given in section 7 on missing data.

Validity of the distributional assumptions for the main analysis model (normal distribution, homoscedasticity) will be assessed with residual analysis. Raw residuals from a covariance pattern model may (compared to a 'standard' linear regression) show both correlation and unequal variances. Raw residuals will be transformed with Cholesky decomposition prior to the assessment described in this section.¹⁸

Histograms and QQ-plots will be created to assess normality of residuals. Residuals will be plotted against raw and normalized predicted values to assess homoscedasticity and linearity. Violation of the assumption of homoscedasticity will be corrected with robust (i.e. Hubert-White's) estimation of standard errors.¹⁸

When a serious violation of the normality assumption is observed in the residual plots, the main analysis will be changed to a mixed regression analysis based on beta distributions.¹⁹ The steps for inclusion of predefined prognostic factors will be included as specified for the primary analysis (see above). Multiple measurements per patient will be corrected with a random intercept. The residual covariance matrix will be excluded from the model, as such models cannot be estimated under maximum likelihood.

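### Section 6.2, read literally, adjusts PROM scores, HbA1c and other continuous non-TIR outcomes for baseline TIR and not for their own month-0 value; the SAP should state which baseline enters

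*SAP*

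**What the plan says.** SAP section 6.1 models TIR "with TIR at 3, 6, 9 and 12 months (hence forward referred to as time) as dependent variable", so month 0 is not part of the response. It describes two analyses. The first contains time, treatment and their interaction. The second adds the "predefined prognostic factors, i.e. TIR at baseline, patients age and sex".

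Section 6.2 opens with "The analysis for continuous secondary outcomes follows the analysis specifications of the primary outcome (see above" and, after the fallbacks for failed distributional assumptions, adds that "all regression analyses will be performed by adjusting for the same a priori defined prognostic factors and repeated measurements". It also says: "Secondary endpoints will be considered supportive and are not included in the formal testing strategy". No p-values are given for these endpoints; linear models are reported as mean differences with 95% CIs.

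Section 4.2 schedules the glycaemic outcomes and the PROMs at month 0 as well as at 3, 6, 9 and 12 months (the hypoglycaemia-awareness score only at 0 and 12). Section 5.3 tabulates the baseline values, and section 7.1 includes them in the imputation.

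**The concern.** The only list of prognostic factors in the SAP is the one in 6.1, and it is closed: baseline TIR, age and sex. If 6.2 carries over that same list, a well-being, sleep or distress score is adjusted for baseline glucose control, while the strongest likely predictor, the patient's own starting score, is left out. It does not enter through the response either, because the response starts at month 3.

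Two things are at stake. Secondary results consist only of estimates and confidence intervals, so interval width is most of what a reader has to judge them by, above all in arm 2 with 35 per group. And two competent analysts could fit different models from the same text, in an open-label trial where such choices are best settled before the data are seen.

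The point does not reach TIR at 3, 6 and 9 months or the TIR-improvement endpoint, for which baseline TIR is the own baseline.

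**Working it through.** **The text.** Three places bear on the covariates.
- 6.1 names them and closes the list.
- The later sentence of 6.2 refers back to that list as the same factors. Literal result: baseline TIR, age, sex.
- The opening sentence of 6.2 refers back to the primary specification as a whole. In 6.1 the outcome is adjusted for its own baseline, so by analogy each secondary outcome would be too.

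Section 7.1 counts secondary outcomes at baseline among the variables to be imputed, which fits the second reading, but it specifies an imputation set and not a model. The text therefore leaves both readings open, and the literal one follows the only sentence that names covariates.

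**Planning inputs.** Sections 3.1 and 3.2 assume TIR SDs of 17 (HCL) versus 4 (DHFCL) with a difference of 7, and 20 (MDI) versus 4 with a difference of 15. A Welch t-test at two-sided 0.05 and 90% power reproduces the stated 68 per group (power 0.904) and 22 per group (power 0.910). These figures do not depend on the point; only the SDs are used below.

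**Formula.** Assume a linear model with one common slope and the same correlation in both groups. For outcome SDs a and b, the average residual variance after adjusting for a baseline covariate with correlation r is proportional to 1 − k·r², with k = (a+b)² / (2(a²+b²)). The CI width with own baseline *in place of* baseline TIR, relative to baseline TIR alone, is

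sqrt((1 − k·r_own²) / (1 − k·r_TIR²)).

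- Equal SDs: k = 1.
- Arm 1: k = 21² / (2 × 305) = 441/610 = 0.723.
- Arm 2: k = 24² / (2 × 416) = 576/832 = 0.692.

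**Assumed correlations.** The SAP gives none. r_own is taken as 0.5 and 0.7, with 0.3 as a weak case for PROMs. For PROM-like outcomes r_TIR is 0.30 down to 0.15. For glycaemic outcomes r_TIR is r_own times the correlation of own baseline with baseline TIR, set at 0.6 (HbA1c-like) and 0.9 (TAR-like).

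| Outcome | r_own = 0.5 | r_own = 0.7 |
|---|---|---|
| PROM-like, k = 1 | sqrt(0.75/0.91) = 0.908 | sqrt(0.51/0.9775) = 0.722 |
| HbA1c-like, arm 1 | 0.936 | 0.860 |
| HbA1c-like, arm 2 | 0.939 | 0.868 |
| TAR-like, arm 1 | 0.980 | 0.952 |
| TAR-like, arm 2 | 0.981 | 0.955 |

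Worked cell, HbA1c-like, arm 1, r_own = 0.5: r_TIR = 0.6 × 0.5 = 0.30, so sqrt((1 − 0.723×0.25)/(1 − 0.723×0.09)) = sqrt(0.819/0.935) = 0.936.

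By formula, intervals are narrower by about 9–28% (PROM-like), 6–14% (HbA1c-like) and 2–5% (TAR-like).

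**Simulation of a neighbouring model.** Here own baseline is *added* to baseline TIR, age and sex, so the results do not check the formula line by line. With 6,000 runs per setting, the ratios of empirical and of robust standard errors ran as follows.
- HbA1c-like: 0.956 to 0.868, or 4–13% narrower.
- TAR-like: 0.997 to 0.956, or 0–4% narrower.
- PROM-like: 0.906 to 0.724, or 9–28% narrower.

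Robust errors are relevant because 6.1 says "Violation of the assumption of homoscedasticity will be corrected with robust" standard errors.

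**Weak case.** For a PROM with r_own = 0.3 and r_TIR of 0.10 to 0.30, adding own baseline gave ratios of 0.963 to 0.988 (1–4%; 3,000 runs). Replacing baseline TIR gives sqrt(0.91/0.99) = 0.959 down to no gain at sqrt(0.91/0.91) = 1.

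**The case against.** The strongest reply is that own baseline was always meant. The opening sentence of 6.2 supports that by analogy, and 7.1 seems to count baseline secondary outcomes among the analysis variables; with a response starting at month 3, they could enter the comparative models only as covariates. This has weight, and it is why the point is an ambiguous back-reference and not a demonstrated wrong model. It does not settle the matter, because 7.1 is about imputation and the sentence that does name the covariates says they are the same ones.

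A second reply is that little depends on it. That largely stands. No decision in the SAP rests on these intervals, and only the covariate-adjusted step of the two-step plan is affected. The sizes rest on assumed correlations, the 28% pairs the highest own-baseline correlation with the lowest TIR correlation, and carrying the TIR planning SDs over to HbA1c or TAR is itself an assumption.

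A reader might infer more: that secondary estimates are biased, that the primary comparison or its error rate is at risk, or that chance baseline imbalance is a separate harm. The SAP does not support this. With randomisation and complete outcomes the linear estimates are unbiased under either reading; the primary model already uses its own baseline; and chance imbalance is part of the precision loss already counted. Dropout that depended on a patient's baseline score could add bias, but nothing in the SAP shows that it will.

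**Conclusion.** The point holds as a low-severity ambiguity. Read literally, 6.2 leaves the own month-0 value out of the adjusted models for continuous non-TIR outcomes; a second reading includes it. The consequence of the literal reading is wider intervals in the adjusted analysis of supportive endpoints.

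Under own-baseline correlations of 0.5–0.7, and taking both ways of entering the own baseline together, the gain is about 9–28% for PROM-like outcomes, 4–14% for HbA1c-like and 0–5% for TAR-like. For PROMs with a correlation of 0.3 it is about 1–4% when own baseline is added and 0–4% when it replaces baseline TIR. The glycaemic figures also need the TIR planning SDs to carry over. No gain is claimed for odds ratios, rate ratios, or the log-transformed, alternative-distribution or non-parametric fallbacks, and no separate figure is given for TBR, CV or mean glucose.

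**What to change.** Add to section 6.2:

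> In the covariate-adjusted analysis, each continuous secondary outcome measured at month 0 is adjusted for its own month-0 value, age and sex, in place of baseline TIR. Comparative outcomes without a usable month-0 value (e.g. DTSQ-c) keep baseline TIR, age and sex.

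This fixes one model per outcome. TIR at 3, 6 and 9 months is unchanged by it. DHFCL-only outcomes (glucagon use, time the algorithm was active) have no control comparison and need no such rule. Because the sentence in 6.2 governs every regression, the SAP should also say which covariates the binary and count models use; the reason there is clarity only.

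The cost is two or three sentences and no new data, since month-0 values are already collected, tabulated and imputed. If own baseline was intended all along, the text only makes that explicit. If baseline TIR is really meant for every outcome, the SAP should say so.

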4.2 Secondary endpoints

Secondary endpoints include other glycaemic outcomes, patient reported outcome measurements, and cost-effectiveness outcomes and safety and device-related outcomes.

4.2.1 Glycaemic control endpoints at 0, 3, 6, 9 and 12 months:

- Time in range (TIR) (3.9-10 mmol/l) (%; amount of time (hours/minutes)) at 3, 6 and 9 months;
- Time above range (TAR):
 - level 1 and 2 hyperglycaemia: % of time spent >10.0 mmol/l;
 - level 2 hyperglycaemia: % of time spent >13.9 mmol/l;
- Time below range (TBR):
 - level 1 and 2 hypoglycaemia: % of time spent <3.9 mmol/l;
 - level 2 hypoglycaemia: % of time spent <3.0 mmol/l;
- Number of hypoglycaemic events: defined as glucose <3.0 mmol/l for 15 consecutive minutes⁶, when the time between two successive events is less than 30 minutes, they will be combined and counted as one event;
- Mean glucose (mmol/l) per patient per time point:
 - o day and night;
 - o day: from 06:00 to 23:59 hours;
 - night: from 00:00 to 05:59 hours;
- Glycaemic variability:
 - Coefficient of variation (%);
 - Standard deviation (mmol/l);
- HbA1c:
 - Mean per patient per time point (mmol/mol);
 - Percentage of patients achieving HbA1c \leq 53 mmol/mol.
- Percentage patients with ≥5% points TIR improvement from baseline (%) at 12 months;
- Percentage patients achieving >70% TIR and/or <4% TBR at 12 months;
- Time in tight range (3.9-7.8 mmol/l) (%; amount of time (hours/minutes).

4.2.2 Patient reported outcome measures (PROMs), at 0, 3, 6, 9 and 12 months:

- World Health Organization-Five Well-Being Index (WHO-5) score;
- Health-related quality of life scores (EQ-5D-5L);
- Diabetes Treatment and Satisfaction Questionnaire status and change (DTSQ-s and DTSQ-c) scores;
- Problem Areas In Diabetes (PAID-5) score;
- Hypoglycaemia Fear Survey-II (HFS-II) Worry subscale score;
- Pittsburgh Sleep Quality Index (PSQI) score;

- Insulin delivery systems: perceptions, ideas, reflections and expectations (INSPIRE) scores; only for HCL and DHFCL groups;
- Hypoglycaemia unawareness (Gold-Clarke): only at 0 and 12 months.

These scores will be calculated as defined previously.^{8–16}

4.2.3 Cost effectiveness endpoints:

- Medical Consumption Questionnaire (MCQ), at 0, 3, 6, 9 and 12 months;
- Productivity Cost Questionnaire (PCQ), at 0, 3, 6, 9 and 12 months;

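### The odds ratio planned for the repeated HbA1c-target endpoint is patient-specific, is not labelled as such, and is not comparable in size with the odds ratios of the 12-month-only binary endpoints

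*SAP*

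**What the plan says.** Section 4.2.1 lists, under a heading that covers 0, 3, 6, 9 and 12 months, the "Percentage of patients achieving HbA1c" at or below 53 mmol/mol. Two other binary endpoints in that list are tied to 12 months: a TIR gain of at least 5 points, and reaching the TIR and/or TBR targets.

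Section 6.2 sets the analysis:

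- Repeated binary outcomes: "Binary secondary outcomes will be analyzed with mixed logistic regression analysis", and "For binary and count outcomes, analyses with a random intercept will initially be performed". The reason given is that such models can be fitted by maximum likelihood.
- Outcomes measured once, at 12 months: models "without adjustment for repeated measurements (i.e. regular linear and logistic regression").
- Covariates: "all regression analyses will be performed by adjusting for the same a priori defined prognostic factors and repeated measurements". Section 6.1 names these factors as baseline TIR, age and sex.
- Reporting: "For binary outcomes, results will be reported as odds ratios with 95% Cls". This sentence covers both kinds of model.

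Section 6.2 does not name the unit of the random intercept. Section 6.1, on the beta-regression fallback, says "Multiple measurements per patient will be corrected with a random intercept". Section 6.2 gives no p-values for secondary endpoints and treats them as supportive.

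**The concern.** The endpoint is a percentage of patients in each group, but the planned comparison is an odds ratio for a patient with a given random intercept. With a logit link these are different quantities whenever patients differ from one another. The patient-specific odds ratio moves away from 1 as between-patient variance grows, even when the group percentages stay the same.

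The continuous outcomes do not have this problem. Section 6.1 uses a residual covariance matrix, so the treatment contrast is a difference in population means, and in a linear model a random intercept would leave that meaning unchanged. In a logistic model it does not. The reason given for the random intercept concerns estimation, not which effect is wanted.

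Two things are at stake. A reader cannot get from the reported odds ratio back to the percentages that the endpoint names. And two binary endpoints with the same percentages could show odds ratios of clearly different size only because one was measured repeatedly. As no p-values are given, the estimate and its interval are all that the reader has for the comparison.

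**Working it through.** The SAP gives no expected percentage, odds ratio or within-patient correlation for any binary endpoint, so there is no figure of its own to reproduce. Everything below rests on assumed values, shown as a range.

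**Step 1. Unit of the random intercept.** Section 6.2 requires adjustment for repeated measurements, and an intercept for centre alone would not provide it. Section 6.1 uses a random intercept for repeated measurements per patient where the residual covariance matrix is dropped. Patient is therefore the natural reading, though it is an inference.

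**Step 2. From percentages to the patient-specific odds ratio.** With u standard normal and random-intercept SD σ on the logit scale, the percentage in group g is

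p_g = E[ expit(η_g + σu) ].

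Solve for η_0 and η_1 so that p_g equals the assumed percentages. The patient-specific odds ratio is then exp(η_1 − η_0). The latent within-patient correlation is σ² / (σ² + π²/3).

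Assume 40% versus 60%. The odds ratio of the percentages is (0.60/0.40) / (0.40/0.60) = 2.25, with log 0.811. Numerical (Gauss-Hermite) integration gives:

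| σ | latent correlation | patient-specific OR | ratio of log ORs |
|---|---|---|---|
| 0.5 | 0.07 | 2.36 | 1.06 |
| 1 | 0.23 | 2.66 | 1.21 |
| 2 | 0.55 | 3.80 | 1.65 |
| 3 | 0.73 | 5.82 | 2.17 |

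In every row the percentages are the same and the risk difference is 20 points.

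A check with the usual approximation, which multiplies the log odds ratio by √(1 + 0.346σ²):

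- σ = 2: √2.384 = 1.54; exp(0.811 × 1.54) ≈ 3.5.
- σ = 3: √4.114 = 2.03; exp(0.811 × 2.03) ≈ 5.2.

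These are somewhat below the exact values, in the same direction and of the same order.

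**Step 3. Comparison with what the SAP plans for 12-month-only endpoints.** Those odds ratios come from logistic regression adjusted for baseline TIR, age and sex, so they are not odds ratios of the raw percentages either. The fair comparison puts a baseline covariate in both models. Large samples were simulated (4,000 per group, four visits) from a continuous outcome cut at a threshold, giving about 40% versus 64%. Both models were fitted by maximum likelihood:

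| latent correlation between visits | raw 12-month OR | ordinary adjusted 12-month OR | adjusted random-intercept OR |
|---|---|---|---|
| 0.5 | 2.5 | 2.7 | 4.1 |
| 0.6 | 2.6 | 3.1 | 4.6 |
| 0.7 | 2.6 | 3.7 | 7.7 |
| 0.8 | 2.7 | 4.5 | 11 |

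The assumed correlation of the covariate with follow-up was 0.1 lower than the between-visit correlation in each row. Adjustment moves the ordinary odds ratio away from the raw one, but the two planned odds ratios still differ for the same underlying outcome.

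**The case against.** The strongest reply is that nothing here is an error. Mixed logistic regression is a standard, valid model for repeated binary data. It uses all available measurements, in line with sections 6.1 and 7.2, and a patient-specific odds ratio is a legitimate effect measure. The endpoint is supportive and has no p-value, so no formal conclusion of the trial depends on it. Only one listed endpoint is clearly both binary and repeated. All of this stands, and it limits the point to reporting.

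Several stronger readings are tempting, and the document does not support them:

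- A reader might infer that the planned odds ratio will be far larger than that of the percentages. That needs strong persistence within patients. It is plausible for HbA1c status every three months, but the SAP gives no variance or correlation, and at SD 0.5 to 1 the gap is modest. The gap is also away from 1, so an odds ratio below 1 would become smaller.
- A reader might say that the odds ratio overstates the difference in percentages. It does not estimate that difference; it is another quantity, not a biased one.
- A reader might take the 12-month odds ratios as a marginal benchmark. They are covariate-adjusted, as step 3 allows for.
- A reader might expect harm to the economic evaluation. Sections 4.2.3 and 6.3 do not link the HbA1c target to it.

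The SAP may also intend to tabulate observed percentages, since section 6.4 foresees descriptive tables. That would help, but crude percentages do not come from the adjusted repeated-measures model and carry no planned contrast or interval.

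**Conclusion.** The point holds as a weakness in the reported summary, not in the model. The odds ratio planned for the HbA1c-target endpoint is patient-specific and lies further from 1 than the odds ratio of the percentages that define the endpoint. It also carries the same label as the odds ratios of the 12-month-only endpoints, with which it is not comparable in size. For an assumed 40% versus 60%, 2.25 becomes 2.36 to 2.66 at a random-intercept SD of 0.5 to 1, 3.8 at SD 2 and 5.8 at SD 3.

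This rests on the random intercept being by patient and on assumed percentages and variances. The direction of the gap does not depend on those assumed values as long as patients vary; its size does. It is a low-cost improvement for supportive endpoints and has no bearing on the primary analysis.

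**What to change.** In section 6.2:

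1. Keep the mixed logistic model and state that its random intercept is by patient, if that is the intention.
2. Label its odds ratio as patient-specific, and label the 12-month-only odds ratios as covariate-adjusted from ordinary logistic regression.
3. For every binary endpoint, also report the model-standardised 12-month percentage in each group and the risk difference with 95% CI. To do this, predict each patient's 12-month probability under each treatment, average over the covariates and, where there is one, integrate over the random intercept. Then take the difference of the two group averages.

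This gives the quantity that the endpoint names, on a scale that can be compared across all binary endpoints. It costs a few sentences in the SAP and one post-estimation step with delta-method or bootstrap intervals. No data collection, sample size or primary analysis changes.
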